8 STUDY SCHEDULE

Complete study schedule details listed by type of visit are described below. Refer also to [Sections 4 and 7](#) as well as [Appendix A: Schedule of Study Procedures and Evaluations](#) and [Appendix B: Schedule of Special Assays](#).

Note: There are two different dosing intervals between the priming (first) and boosting (second) doses (21 days vs. 4 months). Treatment Arms 1 and 4 receive study vaccinations on Days 1 and 22; and Treatment Arms 2, 3, 5, and 6 receive study vaccinations on Days 1 and 121.

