- A urine or serum pregnancy test will be performed locally by the site within 24 hours prior to the second study vaccination for all women of childbearing potential. Results must be negative and known prior to the second study vaccination.
- Approximately 10 mL of venous blood will be collected immediately prior to the second study vaccination for clinical safety labs (WBC, Hgb, PLT, ALT, T. Bili, Cr) to be performed by the central (clinical) laboratory. The results from these evaluations will not be available or reviewed prior to the second study vaccination.
- Approximately 15 mL of venous blood will be collected immediately prior to the second study vaccination for serological assays.
- Approximately 32 mL of venous blood will be collected immediately prior to the second study vaccination for cellular immunology assays.
- Approximately 16 mL of venous blood will be collected immediately prior to the second study vaccination for future research.
- Pre-administration reactogenicity assessments will be performed immediately prior to the second study vaccination to establish baseline.
- Subjects will then receive one- 0.5 mL dose of study vaccine via a single IM injection into the deltoid muscle of the subjects' preferred arm. The second study vaccination may be given in the same preferred arm as long as there is no interference with the reactogenicity assessment. The site of injection (right or left arm) and time of study vaccine administration to the subject will be recorded on the appropriate DCF. Subjects will be observed in the clinic for at least 20 minutes after the second study vaccination.

The second study vaccination site will be examined, post-administration reactogenicity assessments will be performed, and any AE/SAEs will be recorded on the appropriate DCF prior to discharge from the clinic.

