3.2.2. Secondary

Safety:

- Occurrence of all unsolicited non-serious AEs from the time of each study vaccination through approximately 21 days after each study vaccination.
- Occurrence of all MAAEs, including NOCMCs and PIMMCs, from the time of the first study vaccination through approximately 12 months after the last study vaccination.

Immunogenicity:

- For HAI and Neut antibodies, percentage of subjects achieving seroconversion against the influenza A/H7N9 study vaccine viruses approximately 21 days after the first study vaccination as well as immediately prior to and approximately 180 days after the second study vaccination.

- For HAI and Neut antibodies, percentage of subjects achieving titer $\geq 1:40$ against the influenza A/H7N9 study vaccine viruses immediately prior to each study vaccination, approximately 21 days after the first study vaccination and approximately 180 days after the second study vaccination.
- GMTs of serum HAI and Neut antibodies against the influenza A/H7N9 study vaccine viruses immediately prior to each study vaccination, approximately 21 days after the first study vaccination and approximately 180 days after the second study vaccination.

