6.3.3. Per Protocol Population

The per protocol (PP) population includes all subjects in the mITT subset with the following exclusions:

- Data from all available visits for subjects found to be ineligible at baseline.
- Data from all visits subsequent to major protocol deviations, such as:
 - Second study vaccination not received,
 - Second study vaccination received out of window,
 - Receipt of non-study licensed, live vaccine within 30 days before or after each study vaccination,
 - Receipt of non-study licensed, inactivated vaccine within 14 days before or after each study vaccination,
 - Receipt of immunosuppressive therapy (e.g., corticosteroids) within 30 days before or after each study vaccination.
- Data from any visit that occurs out of window by more than one day. However, use exact window for visits that occur either 1 day or 3 days post study vaccinations:
 - Visit 2 data collected before 1 day or after 2 days post first study vaccination.
 - Visit 3 data collected before 3 days or after 4 days post first study vaccination.
 - Visit 4 data collected before 5 days or after 10 days post first study vaccination.
 - Visit 5 data collected before 12 days or after 16 days post first study vaccination.
 - Visit 6 data collected before 20 days or after 29 days post first study vaccination.
 - Visit 7 data collected before 1 day or after 2 days post second study vaccination for study groups 1 and 4.

-
- Visit 8
 - Data collected before 3 days or after 4 days post second study vaccination for study groups 1 and 4.
 - Data collected before 112 days or after 135 days post first study vaccination for study groups 2, 3, 5, and 6.
 - Visit 9
 - Data collected before 5 days or after 10 days post second study vaccination for study groups 1 and 4.
 - Data collected before 1 day or after 2 days post second study vaccination for study groups 2, 3, 5, and 6.
 - Visit 10
 - Data collected before 12 days or after 16 days post second study vaccination for study groups 1 and 4.
 - Data collected before 3 days or after 4 days post second study vaccination for study groups 2, 3, 5, and 6.
 - Visit 11
 - Data collected before 20 days or after 29 days post second study vaccination for study groups 1 and 4.
 - Data collected before 5 days or after 10 days post second study vaccination for study groups 2, 3, 5, and 6.
 - Visit 12
 - Data collected before 53 days or after 67 days post second study vaccination for study groups 1 and 4.

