| | No Baseline Results Available | x | xx | x | xx | x | xx | x | xx | x | xx | x | xx | x | xx |
| | No Day 22 post Vac 1 Result Reported by Lab | x | xx | x | xx | x | xx | x | xx | x | xx | x | xx | x | xx |
| | Lost to Follow-up Before Day 22 post Vac 1 | x | xx | x | xx | x | xx | x | xx | x | xx | x | xx | x | xx |
| | Receipt of Non-Study Vaccination | x | xx | x | xx | x | xx | x | xx | x | xx | x | xx | x | xx |
| | Receipt of Immunosuppressive medication | x | xx | x | xx | x | xx | x | xx | x | xx | x | xx | x | xx |

| Analysis Populations | Reason Subjects Excluded | Group 1 2013 3.75+AS03/ 20173.75+AS03 (D1-D22) (N=X) | | Group 2 2013 3.75+AS03/ 2017 3.75+AS03 (D1-D121) (N=X) | | Group 3 2013 3.75+AS03/ 2017 15 (D1-D121) (N=X) | | Group 4 2017 3.75+AS03/ 2017 3.75+AS03 (D1-D22) (N=X) | | Group 5 2017 3.75+AS03/ 2017 3.75+AS03 (D1-D121) (N=X) | | Group 6 2017 3.75+AS03/ 2017 15 (D1-D121) (N=X) | | All Subjects (N=X) | |
|----------------------------------|--|---|----|--|----|--|----|---|----|--|----|--|----|--------------------------|----|
| | | n | % | n | % | n | % | n | % | n | % | n | % | n | % |
| | Day 22 post Vac 1 Visit Out of Window | x | xx | x | xx | x | xx | x | xx | x | xx | x | xx | x | xx |
| Per Protocol, Day 121 post Vac 1 | Any Reason | NA | NA | x | xx | x | xx | NA | NA | x | xx | x | xx | x | xx |
| | Study Vaccination 1 Not Received | NA | NA | x | xx | x | xx | NA | NA | x | xx | x | xx | x | xx |
| | Study Vaccination 2 Not Received | NA | NA | x | xx | x | xx | NA | NA | x | xx | x | xx | x | xx |
| | Study Vaccination 2 Out of Window | NA | NA | x | xx | x | xx | NA | NA | x | xx | x | xx | x | xx |
| | No Baseline Results Available | NA | NA | x | xx | x | xx | NA | NA | x | xx | x | xx | x | xx |
| | No Day 121 post Vac 1 Result Reported by Lab | NA | NA | x | xx | x | xx | NA | NA | x | xx | x | xx | x | xx |
| | Lost to Follow-up Before Day 121 post Vac 1 | NA | NA | x | xx | x | xx | NA | NA | x | xx | x | xx | x | xx |
| | Receipt of Non-Study Vaccination | NA | NA | x | xx | x | xx | NA | NA | x | xx | x | xx | x | xx |
| | Receipt of Immunosuppressive medication | NA | NA | x | xx | x | xx | NA | NA | x | xx | x | xx | x | xx |
| | Day 121 post Vac 1 Visit Out of Window | NA | NA | x | xx | x | xx | NA | NA | x | xx | x | xx | x | xx |
| Per Protocol, Day 22 post Vac 2 | Any Reason | x | xx | x | xx | x | xx | x | xx | x | xx | x | xx | x | xx |

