16.2.3 Subjects Excluded from the Analysis

Listing 5: 16.2.3: Subjects Excluded from Analysis Populations

[Implementation Note: This data in this listing should be congruent with the “Analysis Populations by Study Group” table. The reasons included here should match the SAP text that describes who will be excluded from analyses.]

| Study Group | Subject ID | Analyses in which Subject is Included | Analyses from which Subject is Excluded | Results Available? | Reason Subject Excluded |
|-------------|------------|---------------------------------------|---|--------------------|-------------------------|
| | | [e.g., Safety, ITT, PP] | [e.g., Safety, ITT, PP, Day x] | | |
| | | | | | |
| | | | | | |
| | | | | | |
| | | | | | |

Note: “Yes” in the “Results available” column indicates that available data were removed from the analysis. “No” indicates that no data were available for inclusion in the analysis.

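### SAP Table 15 excludes the pre-boost Day 121 titer from the per-protocol set on dose-2 grounds that SAP 6.3.3 would not apply to it

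*SAP*

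**What the plan says.** SAP 6.3.3 and Protocol 11.6.1 define the per-protocol set by the same rule. After a major deviation, what is removed is "Data from all visits subsequent to major protocol deviations, such as" a missed second vaccination or one given out of window. Earlier data stay in.

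Protocol 8.2.7 fixes the order of events at the dose-2 visit, for all arms: "Approximately 15 mL of venous blood will be collected immediately prior to the second study vaccination for serological assays". In Groups 2, 3, 5 and 6 this is Visit 08, around Day 121. In Groups 1 and 4 it is Visit 06, because "Treatment Arms 1 and 4 receive study vaccinations on Days 1 and 22". The pre-boost titer is a named secondary endpoint in SAP 3.2.2: "GMTs of serum HAI and Neut antibodies against the influenza A/H7N9 study vaccine viruses immediately prior to each study vaccination".

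SAP Table 15 lists reasons for exclusion separately for each per-protocol timepoint. The Day 121 block contains the rows "Study Vaccination 2 Not Received | NA | NA" and "Study Vaccination 2 Out of Window | NA | NA", filled for Groups 2, 3, 5 and 6. The Day 22 post-first-vaccination block has no row about dose 2 for any group. Listing 5 must be consistent with Table 15, and its note adds: "The reasons included here should match the SAP text that describes who will be excluded from analyses".

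**The concern.** The text and the table shell give two different per-protocol sets at Day 121. Under the text, a titer measured before dose 2 stays in, whatever happens with dose 2. Under the table, it leaves if dose 2 was not given or was given out of window.

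The per-protocol results are meant to show how sensitive the mITT results are to adherence (SAP 8.1). Removing a valid pre-boost titer because of dose 2 does not serve that purpose: non-receipt of dose 2 cannot have altered a sample taken beforehand. At stake are the Day 121 rows of SAP Tables 25, 27, 29 and 31, all marked for the topline set, and the Day 121 points in the per-protocol GMT plots (Figures 7 and 9). SAP Section 12 declares no change from the protocol's analyses, so following the table would be an undeclared departure from Protocol 11.6.1.

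**Working it through.** **1. The plan's own figure.** Protocol 11.4.3 and SAP Section 5 assume up to 10% per-protocol exclusions: 30 × (1 − 0.10) = 27 per group, as in the power table. The figure reproduces, but it does not measure this point (step 5).

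**2. The two pre-boost blocks of Table 15 side by side.**

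| | Groups 1 and 4 | Groups 2, 3, 5 and 6 |
|---|---|---|
| Pre-boost sample | Day 22 after dose 1 | Day 121 after dose 1 |
| Row for dose 2 not given | none | present |
| Row for dose 2 out of window | none | present |
| Row for no laboratory result | present ("No Day 22 post Vac 1 Result Reported by Lab") | present |
| Row for lost to follow-up | present | present |
| Row for visit out of window | present | present |

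Absent and late samples already have their own rows, so what the two extra rows can add is the removal of results that exist and were collected in the visit window.

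**3. The rule applied to the sample.** The draw precedes dose 2. Non-receipt, or receipt outside the window, is therefore not established until after the draw. Visit 08 is not a visit subsequent to the deviation, and SAP 6.3.3 keeps the titer.

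**4. What the out-of-window row can add.** SAP 4.4.5 gives a dose-2 window of 113 to 134 days for the 4-month groups. SAP 6.3.3 accepts Visit 08 data from day 112 to day 135. With the draw and the dose on the same day, the visit passes while the dose fails only on the days in the second range but not the first: 112 and 135. This assumes that the one-day visit tolerance does not extend to the dose, which SAP 6.3.3 does not say.

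**5. How many subjects.** Protocol 11.4.2 expects about 10% exclusions in the 4-month arms: 0.10 × 30 = 3 per group. That figure concerns the primary outcome 21 days after dose 2 and covers all causes, including loss to follow-up, where there may be no Day 121 titer to lose. Protocol 5.2.4 asks one-dose subjects for serum about 21 and 180 days after their last dose and does not name Day 121. Protocol 8.2.7 does allow a discontinued subject to attend the dose-2 visit for safety follow-up. So 3 per group is a loose upper bound at the planning rate, and the documents yield no estimate below it.

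**6. Illustration of the effect.** Let k of 30 titers be removed, and let the removed subjects lie d doublings below those kept (d is assumed; the documents give no value). The all-available mean log2 titer is then lower than the per-protocol mean by k × d / 30, so the per-protocol GMT divided by the all-available GMT is 2^(d × k / 30).

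- k = 1; d = 1, 2, 3: ratio 1.02, 1.05, 1.07
- k = 3; d = 1, 2, 3: ratio 1.07, 1.15, 1.23

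If the removed subjects lie above those kept, the ratios invert.

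**The case against.** The best reply is that Table 15 is a mock-up. Its note tells the programmer to omit reasons not observed, and the Listing 5 note points to the SAP text. If the text governs, the two rows would come out empty and disappear. This carries weight, but the same Listing 5 note also demands agreement with Table 15. For a Day 121 sample without dose 2 both cannot be satisfied, and the SAP does not say which prevails.

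The reply is stronger on consequence. The mITT population is primary and keeps these titers. Per-protocol displays depend on a 10% exclusion trigger. Day 121 is neither a regression time point (SAP 8.3.2) nor a panel of the distribution curves, and no formal testing is planned for secondary endpoints (SAP 8.2). The out-of-window row matters on two days only, and Protocol 6.3 allows no exception to the dose window. All of this stands.

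Three stronger readings are tempting, and the documents do not support them:

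- **Scale.** A reader might multiply 10% by the 120 subjects in the 4-month arms and say that 12 valid titers are lost. Step 5 shows that the 10% does not count such subjects.
- **Bias.** A reader might infer that the Day 121 estimate is biased through reactions to the prime. Dose 2 can be withheld for adverse events, new illness or hospitalization (Protocol 5.2.3), but most such reasons arise before or at Visit 08, and a link to titer is conjecture.
- **Comparability.** A reader might conclude that the 21-day and 4-month arms cannot be compared. Day 121 is not applicable to Groups 1 and 4 in Table 24, and the four groups that have it share one rule. The Day 22 sample in Groups 1 and 4 also serves the separate endpoint 21 days after dose 1, which needs no dose 2 and explains why that block has no such row.

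**Conclusion.** The inconsistency holds: the Day 121 block of Table 15 lists two exclusion reasons that SAP 6.3.3 and Protocol 11.6.1 would not apply to a sample drawn before dose 2. If the shell is programmed as drawn, valid pre-boost titers leave the per-protocol Day 121 summaries for subjects bled at Visit 08 who did not receive dose 2, and for any bled and dosed on day 112 or 135.

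The effect is limited to secondary, descriptive, per-protocol results. The number affected is probably small; that is a judgment from the follow-up arrangements and not a derived figure. The ratios in step 6 rest on assumed titer gaps and show possible size only; the direction is unknown. The primary mITT analysis does not change. The point deserves correction because the two sources lead to different analysis sets and the change costs almost nothing.

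**What to change.** In the Day 121 post-first-vaccination block of SAP Table 15, delete the rows for dose 2 not received and dose 2 out of window. Align the Listing 5 derivation with SAP 6.3.3, so that a Day 121 sample is excluded only for baseline ineligibility, a deviation that precedes it, or a visit outside days 112 to 135. Missing results and loss to follow-up keep their own rows. Retain the dose-2 reasons in the Day 22 and Day 181 post-second-vaccination blocks, where SAP 6.3.3 does apply them.

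The cost is two shell rows and one derivation line. No visit, sample or treatment changes.

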14.1.2 Demographic Data by Study Group

Table 19: Summary of Categorical Demographic and Baseline Characteristics by Site, All Enrolled Subjects

| Variable | Characteristic | [Site 1] (N=X) | | [Site 2] (N=X) | | [Site 3] (N=X) | | [Site 4] (N=X) | | [Site 5] (N=X) | | [Site 6] (N=X) | | All Subjects (N=X) | |
|--|---|-------------------|----|-------------------|----|-------------------|----|-------------------|----|-------------------|----|-------------------|----|--------------------------|----|
| | | n | % | n | % | n | % | n | % | n | % | n | % | n | % |
| Sex | Male | x | xx | x | xx | x | xx | x | xx | x | xx | x | xx | x | xx |
| | Female | | | | | | | | | | | | | | |
| BMI | < 30 | | | | | | | | | | | | | | |
| | ≥ 30 | | | | | | | | | | | | | | |
| Ethnicity | Not Hispanic or Latino | x | xx | x | xx | x | xx | x | xx | x | xx | x | xx | x | xx |
| | Hispanic or Latino | | | | | | | | | | | | | | |
| | Not Reported | | | | | | | | | | | | | | |
| | Unknown | | | | | | | | | | | | | | |
| Race | American Indian or Alaska Native | x | xx | x | xx | x | xx | x | xx | x | xx | x | xx | x | xx |
| | Asian | | | | | | | | | | | | | | |
| | Native Hawaiian or Other Pacific Islander | | | | | | | | | | | | | | |
| | Black or African American | | | | | | | | | | | | | | |
| | White | | | | | | | | | | | | | | |
| | Multi-Racial | | | | | | | | | | | | | | |
| | Unknown | | | | | | | | | | | | | | |
| Prior Seasonal Influenza Vaccination (Prior Seasons) | 2016-2017 Received | | | | | | | | | | | | | | |
| | 2016-2017 Not Received | | | | | | | | | | | | | | |

| Variable | Characteristic | [Site 1] (N=X) | | [Site 2] (N=X) | | [Site 3] (N=X) | | [Site 4] (N=X) | | [Site 5] (N=X) | | [Site 6] (N=X) | | All Subjects (N=X) | |
|--|---|-------------------|---|-------------------|---|-------------------|---|-------------------|---|-------------------|---|-------------------|---|--------------------------|---|
| | | n | % | n | % | n | % | n | % | n | % | n | % | n | % |
| | 2016-2017 Unknown | | | | | | | | | | | | | | |
| | 2017-2018 Received | | | | | | | | | | | | | | |
| | 2017-2018 Not Received | | | | | | | | | | | | | | |
| | 2017-2018 Unknown | | | | | | | | | | | | | | |
| Seasonal Influenza Vaccination (Current Season) | 2018-2019 Received | | | | | | | | | | | | | | |
| | 2018-2019 Not Received | | | | | | | | | | | | | | |
| | 2018-2019 Unknown | | | | | | | | | | | | | | |
| Prior Receipt of H5 Influenza Vaccine | No Prior H5 Influenza Vaccination(s) | | | | | | | | | | | | | | |
| | Received Prior H5 Influenza Vaccination(s) | | | | | | | | | | | | | | |
| N= Number of subjects enrolled. | | | | | | | | | | | | | | | |

Table 20: Summary of Continuous Demographic and Baseline Characteristics by Site, All Enrolled Subjects

| Variable | Statistic | [Site 1] (N=X) | [Site 2] (N=X) | [Site 3] (N=X) | [Site 4] (N=X) | [Site 5] (N=X) | [Site 6] (N=X) | All Subjects (N=X) |
|---------------------------------|--------------------|-------------------|-------------------|-------------------|-------------------|-------------------|-------------------|-----------------------|
| Age | Mean | x.x | x.x | x.x | x.x | x.x | x.x | x.x |
| | Standard Deviation | x.x | x.x | x.x | x.x | x.x | x.x | x.x |
| | Median | x.x | x.x | x.x | x.x | x.x | x.x | x.x |
| | Minimum | x | x | x | x | x | x | x |
| | Maximum | x | x | x | x | x | x | x |
| BMI | Mean | x.x | x.x | x.x | x.x | x.x | x.x | x.x |
| | Standard Deviation | x.x | x.x | x.x | x.x | x.x | x.x | x.x |
| | Median | x.x | x.x | x.x | x.x | x.x | x.x | x.x |
| | Minimum | x | x | x | x | x | x | x |
| | Maximum | x | x | x | x | x | x | x |
| N= Number of subjects enrolled. | | | | | | | | |

Table 21: Summary of Categorical Demographic and Baseline Characteristics by Study Group, All Enrolled Subjects

| Variable | Characteristic | Group 1 2013 3.75+AS03/ 2017 3.75+AS03 (D1-D22) (N=X) | | Group 2 2013 3.75+AS03/ 2017 3.75+AS03 (D1-D121) (N=X) | | Group 3 2013 3.75+AS03/ 2017 15 (D1-D121) (N=X) | | Group 4 2017 3.75+AS03/ 2017 3.75+AS03 (D1-D22) (N=X) | | Group 5 2017 3.75+AS03/ 2017 3.75+AS03 (D1-D121) (N=X) | | Group 6 2017 3.75+AS03/ 2017 15 (D1-D121) (N=X) | | All Subjects (N=X) | |
|-----------|---|---|----|--|----|--|----|---|----|--|----|--|----|--------------------------|----|
| | | n | % | n | % | n | % | n | % | n | % | n | % | n | % |
| Sex | Male | x | xx | x | xx | x | xx | x | xx | x | xx | x | xx | x | xx |
| | Female | | | | | | | | | | | | | | |
| BMI | < 30 | | | | | | | | | | | | | | |
| | ≥ 30 | | | | | | | | | | | | | | |
| Age | 19-34 | x | xx | x | xx | x | xx | x | xx | x | xx | x | xx | x | xx |
| | 35-50 | | | | | | | | | | | | | | |
| Ethnicity | Not Hispanic or Latino | x | xx | x | xx | x | xx | x | xx | x | xx | x | xx | x | xx |
| | Hispanic or Latino | | | | | | | | | | | | | | |
| | Not Reported | | | | | | | | | | | | | | |
| | Unknown | | | | | | | | | | | | | | |
| Race | American Indian or Alaska Native | x | xx | x | xx | x | xx | x | xx | x | xx | x | xx | x | xx |
| | Asian | | | | | | | | | | | | | | |
| | Native Hawaiian or Other Pacific Islander | | | | | | | | | | | | | | |
| | Black or African American | | | | | | | | | | | | | | |
| | White | | | | | | | | | | | | | | |

| Variable | Characteristic | Group 1 2013 3.75+AS03/ 2017 3.75+AS03 (D1-D22) (N=X) | | Group 2 2013 3.75+AS03/ 2017 3.75+AS03 (D1-D121) (N=X) | | Group 3 2013 3.75+AS03/ 2017 15 (D1-D121) (N=X) | | Group 4 2017 3.75+AS03/ 2017 3.75+AS03 (D1-D22) (N=X) | | Group 5 2017 3.75+AS03/ 2017 3.75+AS03 (D1-D121) (N=X) | | Group 6 2017 3.75+AS03/ 2017 15 (D1-D121) (N=X) | | All Subjects (N=X) | |
|---|------------------------|---|---|--|---|--|---|---|---|--|---|--|---|--------------------------|---|
| | | n | % | n | % | n | % | n | % | n | % | n | % | n | % |
| | Multi-Racial | | | | | | | | | | | | | | |
| | Unknown | | | | | | | | | | | | | | |
| Prior Seasonal Influenza Vaccination (Prior Seasons) | 2016-2017 Received | | | | | | | | | | | | | | |
| | 2016-2017 Not Received | | | | | | | | | | | | | | |
| | 2016-2017 Unknown | | | | | | | | | | | | | | |
| | 2017-2018 Received | | | | | | | | | | | | | | |
| | 2017-2018 Not Received | | | | | | | | | | | | | | |
| | 2017-2018 Unknown | | | | | | | | | | | | | | |
| Seasonal Influenza Vaccination (Current Season) | 2018-2019 Received | | | | | | | | | | | | | | |
| | 2018-2019 Not Received | | | | | | | | | | | | | | |
| | 2018-2019 Unknown | | | | | | | | | | | | | | |

| Variable | Characteristic | Group 1 2013 3.75+AS03/ 2017 3.75+AS03 (D1-D22) (N=X) | | Group 2 2013 3.75+AS03/ 2017 3.75+AS03 (D1-D121) (N=X) | | Group 3 2013 3.75+AS03/ 2017 15 (D1-D121) (N=X) | | Group 4 2017 3.75+AS03/ 2017 3.75+AS03 (D1-D22) (N=X) | | Group 5 2017 3.75+AS03/ 2017 3.75+AS03 (D1-D121) (N=X) | | Group 6 2017 3.75+AS03/ 2017 15 (D1-D121) (N=X) | | All Subjects (N=X) | |
|---|---|---|---|--|---|--|---|---|---|--|---|--|---|--------------------------|---|
| | | n | % | n | % | n | % | n | % | n | % | n | % | n | % |
| Prior Receipt of H5 Influenza Vaccine | No Prior H5 Influenza Vaccinations | | | | | | | | | | | | | | |
| | Received Prior H5 Influenza Vaccinations | | | | | | | | | | | | | | |
| N= Number of subjects enrolled. | | | | | | | | | | | | | | | |

Table 22: Summary of Continuous Baseline Characteristics by Study Group, All Enrolled Subjects

| Variable | Statistic | Group 1 2013 3.75+AS03/ 2017 3.75+AS03 (D1-D22) (N=X) | Group 2 2013 3.75+AS03/ 2017 3.75+AS03 (D1-D121) (N=X) | Group 3 2013 3.75+AS03/ 2017 15 (D1-D121) (N=X) | Group 4 2017 3.75+AS03/ 2017 3.75+AS03 (D1-D22) (N=X) | Group 5 2017 3.75+AS03/ 2017 3.75+AS03 (D1-D121) (N=X) | Group 6 2017 3.75+AS03/ 2017 15 (D1-D121) (N=X) | All Subjects (N=X) |
|---------------------------------|--------------------|--|---|--|--|---|--|-----------------------------------|
| Age | Mean | x.x | x.x | x.x | x.x | x.x | x.x | x.x |
| | Standard Deviation | x.x | x.x | x.x | x.x | x.x | x.x | x.x |
| | Median | x.x | x.x | x.x | x.x | x.x | x.x | x.x |
| | Minimum | x | x | x | x | x | x | x |
| | Maximum | x | x | x | x | x | x | x |
| BMI | Mean | x.x | x.x | x.x | x.x | x.x | x.x | x.x |
| | Standard Deviation | x.x | x.x | x.x | x.x | x.x | x.x | x.x |
| | Median | x.x | x.x | x.x | x.x | x.x | x.x | x.x |
| | Minimum | x | x | x | x | x | x | x |
| | Maximum | x | x | x | x | x | x | x |
| N= Number of subjects enrolled. | | | | | | | | |

